### 9.2.9 Handling of values below a threshold

For the calculation of qRT-PCR parameters, any value which is not recorded as a number but expressed as a value below a detection limit will be imputed by half the value of the declared detection limit itself. For samples reported as qRT-PCR negative the value will be imputed to zero.

qRT-PCR examples:

- If the database contains values like [REDACTED] will be used for calculating parameters.
- If the database contains values like “NEG”, zero will be used for calculating parameters.

For the calculation of TCID50 parameters, any value which is not recorded as a number but expressed as a value below a detection limit will be imputed to half the value of the declared detection limit for the first sample and the remainder values expressed as a value below a detection limit will be imputed to zero. qPCR negative samples that are not tested for TCID50 will be imputed to zero.

TCID50 example:

- If the database contains [REDACTED] the following rules will be used for calculating parameters
  - [REDACTED]
  - [REDACTED]

### 9.2.10 Time to Resolution of Viral Load

Two analyses of median time to resolution of viral load, as determined by qRT-PCR or TCID50 results, and the 95% CI about the median, will be presented using Kaplan-Meier methods. Additional exploratory statistical analyses will be conducted to determine the differences in Kaplan-Meier curves using a log-rank test. Time to resolution of viral load will be assessed on all samples in the MITT population collected through the Day 7 visit for TCID50 analysis and

January 17, 2019

through the Day 14 visit for qRT-PCR analysis. For missing data on Day 1 post-dose, Day 3, Day 5, and Day 7, the analysis will be conducted without imputation and with the last observable measurement carried forward (LOCF). For missing data on Day 1 predose, the analysis will be conducted by replacing the missing data with the Day 1 post-dose observable measurement. Subjects missing both Day 1 predose and Day 1 post-dose virology data will be removed from the analysis. Resolution of viral load is considered to be one BLQ or lower measurement with no samples following that which are greater than the BLQ.

The following virology parameters will be derived:

- Time to resolution of viral load from end of infusion
  - Number of days from end of infusion until virus is no longer detectable (at or below the limit of detection) with no samples following that are greater than the BLQ through the Day 7 (TCID50) or Day 14 (PCR) visit
  - If virus is still above level of detection at Day 7 (TCID50) or Day 14 (PCR) visit, the value will be censored the on Day 7 visit for TCID50 or Day 14 (PCR)
- Time to resolution of viral load from onset of symptoms
  - Number of days from onset of symptoms until virus is no longer detectable (at or below the limit of detection) with no samples following that are greater than the BLQ through the Day 7 (TCID50) or Day 14 (PCR) visit
  - If virus is still above level of detection at Day 7 (TCID50) or Day 14 (PCR) visit, the value will be censored the on Day 7 visit for TCID50 or Day 14 (PCR)

The above analysis will also be performed for the MITT subset comprised of subjects with a positive baseline viral culture based on TCID50.

## 10 PHARMACOKINETIC ANALYSES

Standard non-compartmental approaches using Phoenix WinNonlin (Certara USA, Princeton, NJ, USA; Version 7.0 or higher) will be used to estimate PK parameters in serum and from nasopharyngeal secretions as described below. All calculations will use the actual times recorded in the EDC system for dosing and sampling. Values below the BLQ will be set to 0. Individual and mean ( $\pm$  SD) or median concentrations versus time profiles will be plotted on both linear and logarithmic scales. Additional plots and PK parameters may be generated as appropriate.

The following PK parameters will be determined for VIS410 in serum (all subjects) and/or from nasopharyngeal secretions (only in the first 50 subjects enrolled):

- $C_{\max}$  (ng/ml): maximum observed concentration
- $T_{\max}$  (day): time of  $C_{\max}$
- $T_{\text{last}}$  (day): time of the last measurable concentration
- $AUC_{0-\infty}$  (day\*ug/mL): area under the concentration-time curve from time 0 extrapolated to infinity
- $AUC_{\% \text{extrap}}$  (%): percent extrapolated to  $AUC_{0-\infty}$
- $AUC_{0-\text{last}}$  (day\*ug/mL): area under the concentration-time curve from time 0 to the last measurable concentration

January 17, 2019

- $t_{1/2}$  (day): terminal elimination half-life
  - CL (ml/day): total clearance (serum only)
- $V_d$  (ml): volume of distribution (serum only) Ratio of nasal: serum AUC in subjects with both values available. The nasal:serum ratio will be calculated with both  $AUC_{0-last}$  and with  $AUC_{0-\infty}$

Additional PK parameters may be determined as appropriate.

Plasma and nasal concentration data will be analyzed using Phoenix 7.0 or higher. Individual time points for the terminal slope will automatically be selected by the software, and linear-linear interpolation calculation method will be used for the analysis. No value for  $t_{1/2}$  or other terminal slope dependent parameters (ex.  $AUC_{0-\infty}$  and CL) will be reported for concentration profiles that do not exhibit an elimination phase in individual concentration versus time profiles (at least 3 concentration measurements following  $C_{max}$ ) or if the fit of the terminal slope data is poor (i.e., if adjusted  $R^2 < 0.800$  for the log-linear regression analysis of  $\lambda_z$ ). If the extrapolated portion of  $AUC_{inf}$  from time of last measurable plasma concentration to infinity ( $AUC\%extrap$ ) for a subject is greater than 20.0%, the  $AUC_{0-\infty}$  related PK parameters (ex. CL and  $V_d$ ) will be excluded. No imputation for missing PK data will be performed. BLQ PK samples prior to  $T_{max}$  will be set to 0 in the NCA analysis datasets. All BLQ PK samples following  $T_{max}$  will be set to missing in the analysis dataset.

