1.3.1.1 Pharmacokinetic Results

PK profiles of the serum and nasopharyngeal samples demonstrated that VIS410 exposure was approximately proportional to the dose administered with a mean serum $t_{1/2}$ of 12.9 days. This $t_{1/2}$ is within the expected range for the IgG1 molecules. In addition, the 13-day $t_{1/2}$ supports the single dosing of VIS410, as the circulating levels should be sufficiently high during the normal course of an influenza infection in hospitalized patients (5–14 days). The maximum concentration (C_{max}) values in the serum for the 30- and 50-mg/kg cohorts were 980 and 1316 $\mu\text{g/mL}$, respectively.

Nasopharyngeal swabs were taken from the 15-, 30-, and 50-mg/kg cohorts for upper respiratory PK. The nasopharyngeal PK profiles were approximately dose proportional. Mean nasal C_{max} values at the 30- and 50-mg/kg dose levels were 20.0 and 25.3 $\mu\text{g/mL}$, respectively.

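### The AUC0-last version of the nasal:serum ratio has no common time window, so it is distorted in any subject whose last measurable nasal and serum samples fall on different days

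*SAP*

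**What the plan says.** SAP section 10 gives one list of non-compartmental parameters for serum and nasopharyngeal profiles; the nasal ones are derived "only in the first 50 subjects enrolled". In that list AUC0-last is the "area under the concentration-time curve from time 0 to the last measurable concentration" and Tlast is the "time of the last measurable concentration". Both are properties of a single profile.

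The list ends with the "Ratio of nasal: serum AUC in subjects with both values available. The nasal:serum ratio will be calculated with both" AUC0-last and AUC0-∞. Two ratios are therefore planned. Neither section 10 nor section 10.2 sets an interval over which numerator and denominator should both be taken.

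The handling rules in section 10 fix where each area ends. Samples below the limit after Tmax "will be set to missing in the analysis dataset", missing PK data are not imputed, and the area rule is stated as: "linear-linear interpolation calculation method will be used for the analysis". Where more than 20.0% of AUC0-∞ is extrapolated, the parameters related to it are excluded. No terminal-slope parameter is reported without at least three concentrations after Cmax and an adequate fit.

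In the first 50 subjects, swabs are scheduled at predose, end of infusion and Days 3, 5, 7, 14, 28 and 56 (SAP 10.2). Serum PK is scheduled at baseline, end of infusion and Days 5, 14, 28 and 56 (SAP 16.2; protocol Table 1).

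**The concern.** A ratio of two areas measures relative exposure only if both areas cover the same days. Here each stops at its own Tlast. If nasal drug becomes unmeasurable first, the denominator keeps accumulating serum exposure over days that contribute nothing to the numerator. A missed late swab does the same, and a missed late serum sample does the opposite.

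Unequal Tlast values are plausible. Protocol 1.3.1.1 reports mean nasal peaks of 20.0 and 25.3 µg/mL, while the serum peaks "for the 30- and 50-mg/kg cohorts were 980 and 1316" µg/mL, so nasal drug starts at about 2% of serum. Swabs and blood samples are also separate collections, with late ones taken at outpatient visits. A nasal Tlast on Day 3 or 7 cannot coincide with a serum Tlast, because serum PK is not scheduled on those days.

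At stake is the reading of how much antibody reaches the upper airway. Protocol 1.5.3 says that doses above 2300 mg may be needed, for some strains, to reach an adequate concentration at the site of infection.

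**Working it through.** The plan states no ratio, so there is no figure to reproduce. The question is how far the specified ratio departs from one taken over a common interval.

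**Inputs from the documents.** Serum half-life 12.9 days; 30 mg/kg peaks of 980 (serum) and 20.0 µg/mL (nasal) (protocol 1.3.1.1); the sampling days above, with Day d taken as d − 1 days after dosing.

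**Assumptions.** Mono-exponential decline and serum measurable to Day 56. For the second and third checks, a nasal half-life of 12.9 days is also assumed. The nasal quantification limit (LLOQ) is unknown.

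**1. Closed form.** The AUC0-last ratio divided by the same-interval ratio equals serum AUC to nasal Tlast over serum AUC to serum Tlast:

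(1 − e^(−kt)) / (1 − e^(−55k)), with k = ln 2 / 12.9 = 0.0537 per day.

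- Day 28 (t = 27): 0.766 / 0.948 = 0.808, or 19% low.
- Day 14 (t = 13): 0.503 / 0.948 = 0.530, or 47% low.
- Day 7 (t = 6): 0.276 / 0.948 = 0.291, or 71% low.

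The nasal half-life cancels from this factor. In the reverse case (serum Tlast Day 28, nasal to Day 56, equal half-lives) the ratio is 1 / 0.808 = 1.24, or 24% high.

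**2. Linear trapezoids at the scheduled times.** The ratio in the model is 20 / 980 = 0.0204.

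| Nasal Tlast | AUC0-last ratio | Relative to 0.0204 | Common-interval ratio, relative | AUC0-∞ ratio, relative | Nasal AUC extrapolated |
|---|---|---|---|---|---|
| Day 56 | 0.0203 | 0.996 | 0.996 | 0.996 | 5.0% |
| Day 28 | 0.0159 | 0.780 | 0.995 | 0.965 | 23.1% |
| Day 14 | 0.0103 | 0.504 | 0.993 | 0.953 | 49.7% |
| Day 7 | 0.0056 | 0.274 | 0.998 | 0.951 | 72.6% |

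The shortfalls are 22%, 50% and 73%. Cutting both areas at nasal Tlast removes almost all of it (for Day 7, the serum value was taken from the model). A nasal Tlast of Day 28 or earlier puts the nasal extrapolated share above 20%.

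**3. LLOQ these cases would need.** Nasal concentration at the next scheduled swab is 20 × e^(−k(t − 2/24)): 1.05 µg/mL at Day 56, 4.71 at Day 28 and 9.99 at Day 14. The LLOQ would have to exceed these for Tlast to be Day 28, 14 or 7.

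**4. Against total exposure.** With equal half-lives the same-interval and total-exposure ratios coincide. If nasal half-life were 5 days (an assumption), the nasal exposure after Day 28, 14 and 7 would be 2.4%, 16.5% and 43.5% of its total, and 5.2% of serum exposure lies after Day 56. The AUC0-last ratio relative to the total-exposure ratio is then 0.976 / 0.948 = 1.03, 0.835 / 0.948 = 0.88 and 0.565 / 0.948 = 0.60.

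**The case against.** **Early nasal drop-out is not documented.** Both matrices are scheduled to Day 56 in the first 50 subjects and no LLOQ is given. The Day 7 case needs an LLOQ near 10 µg/mL, half the 30 mg/kg peak. Protocol 1.3.1.1 describes approximately dose-proportional nasal profiles that included the 15 mg/kg cohort, whose proportional peak would be 20.0 × 15/30 = 10 µg/mL, so an LLOQ that high is hard to credit. This stands: a reader might infer that the trial's ratio will be low by these percentages, and the documents do not support that.

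**A second ratio is planned.** The AUC0-∞ ratio is not cut at Tlast, so it would be wrong to say that the nasal:serum ratio as a whole is biased low. It is only a partial safeguard. The 20% rule speaks of plasma and gives clearance and volume, both serum-only, as examples, so its reach to nasal profiles is unclear. If it applies, it removes the subjects with early nasal Tlast and leaves a selected subset.

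**The reference matters.** The large percentages are against a same-interval ratio. If nasal drug drops out because it clears faster, the loss against total exposure is smaller, as step 4 shows. This also stands.

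**Importance.** The ratio is not a listed objective or endpoint, and nasal concentrations, Cmax, AUC and half-life are reported directly. Exposure-response in SAP 11.3 uses serum exposure only. About 33 of the first 50 subjects would be on VIS410 (50 × 2/3). A reader might infer that the ratio will mimic a dose difference in penetration. Doubling the dose does keep nasal drug measurable about one half-life longer, but whether that moves Tlast to a later scheduled swab depends on the unknown LLOQ.

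**Existing provisions.** Section 10 allows additional PK parameters, and Tlast is reported, so a mismatch could be seen. Neither corrects the ratio as specified. Nor does the rule elsewhere in sections 10 and 10.2 that sets values below the limit to 0, because AUC0-last by definition still ends at the last measurable sample.

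**Conclusion.** The point holds for the AUC0-last version only. That ratio has no common window and is distorted in any subject with unequal Tlast values: low against a same-interval ratio if nasal ends first, high if serum ends first. The shortfall would be about 19–22%, 47–50% or 71–73% for a nasal Tlast of Day 28, 14 or 7. Each range runs from the closed form to the trapezoid calculation, assumes a 12.9-day half-life in both matrices and has serum measured to Day 56. There is essentially no error if both are measurable to Day 56.

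Which of these cases will arise cannot be told from the documents, so neither a fixed percentage nor a fixed direction for the trial should be claimed. The consequence is limited to an exploratory PK summary in the first 50 subjects; the primary efficacy analysis is untouched.

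**What to change.** In SAP section 10, define the AUC0-last ratio as a ratio of partial AUCs over one interval in both matrices. Use a fixed window such as Day 1 to Day 14 where both are measurable throughout, and otherwise run to the earlier of the two Tlast values. Keep every sample in each matrix rather than restricting to shared days, which would discard the nasal Day 3 and Day 7 samples. Interpolate serum where the interval ends on a day without a serum sample.

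Report the interval used for each subject. State whether the 20% extrapolation rule applies to nasal profiles, and report by dose group how many subjects are excluded from the AUC0-∞ ratio.

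The cost is a few sentences of SAP text and a partial-AUC request in the software already named. No new data are needed.

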### 10.1 Serum Pharmacokinetics

Serum concentrations will be listed by subject for VIS410 and summary statistics by group will be presented, including means, geometric means, SDs, coefficient of variation (CV), medians, and ranges, as appropriate. Summary graphs, including mean concentration-time profiles by group, will also be presented. Noncompartmental PK parameters will be summarized by group and displayed graphically. The serum concentration data may also be analyzed by population PK methods using nonlinear mixed effects modeling as implemented in NONMEM or equivalent software. Population PK analysis will be performed to describe the time course of serum concentrations of VIS410, and may be pooled with data from prior studies. The influence of covariates on PK parameters will be investigated, if necessary and appropriate.

Additional analyses and summaries may be generated as appropriate.

Results of population PK or PK/PD analyses may be reported outside the CSR

### 10.2 Pharmacokinetics of Nasopharyngeal Secretions and Tracheal Aspirate

Nasopharyngeal swabs will be obtained from both nostrils (1 swab per nostril). The first 50 randomized subjects will have nasopharyngeal swabs collected up to Day 56 (predose, end of infusion, Days 3, 5, 7, 14, 28 and 56); while in the remaining subjects, nasopharyngeal swabs will be obtained up to Day 14 only. If the subject remains in the hospital on Day 10, then additional nasopharyngeal swabs will be obtained on Day 10. Tracheal aspirates will be collected only if subject is intubated and only obtained at Day 1 pre-dose, post-dose, Day 3, Day 5, and Day 7 or at other timepoints per investigator's request. The VIS410 concentrations in the nasopharyngeal secretions and tracheal aspirate will be listed by subject, and summary statistics by group will be reported as described for the serum concentrations. Values less than the BLQ

January 17, 2019

will be set to 0. The computed noncompartmental PK parameters will be listed by subject for VIS410. Summary statistics and PK parameters will be presented, including means, geometric means, standard deviations, CV, medians, and ranges, as appropriate. Summary graphs, including mean concentration-time profiles by group, will also be presented. The nasopharyngeal concentration data may also be analyzed by population PK methods using nonlinear mixed effects modeling as implemented in NONMEM or equivalent software. If necessary, the data may be pooled with data from previous studies for the nonlinear mixed effects (NLME) modeling only. Additional analyses and summaries may be generated as appropriate. Results of population PK or PK/PD analyses may be reported outside the CSR.

## 11 OTHER SECONDARY AND EXPLORATORY ANALYSES

### 11.1 Anti-influenza A Antibodies

Titer of anti-influenza A antibodies (H1 and H3 strains) will be summarized at Baseline (Day 1) and Day 28 with n, mean, SD, geometric mean, CV, minimum and maximum by visit and treatment group for the MITT population. Values below the limit of quantification (BLQ) will be listed as <BLQ and summarized as “5”. Values that are <10 (LLOQ) will be assessed as 5 and values >10240 (ULOQ) will be assessed as 10240. If baseline serum samples are not available for HAI titration, Day 3 values may be imputed back to baseline, if HAI  $\leq$  40.

### 11.2 Resistance Analysis

Genotypic and phenotypic assessment will be conducted to determine the emergence of VIS410-resistant viruses. Sample selection for genotypic testing will be based on primary virology qPCR data. Phenotypic analysis will be performed based on the genotypic analysis. Results will be summarized in a separate genotypic report and a phenotypic report.

### 11.3 Exploratory Pharmacokinetic/Pharmacodynamic Analyses

Associations between serum VIS410 PK exposure parameters (AUC,  $C_{\max}$ ) with virology endpoints will be evaluated. The dependent variables (endpoints) which will be explored in this analysis will include:

- Viral Load AUC (TCID50 and qRT-PCR)
- Post-Baseline Peak Duration of viral shedding (TCID50, qRT-PCR)
- Proportion of subjects with undetectable viral load by group and study day (TCID50, qRT-PCR)
- Proportion of subjects with undetectable viral load by group and study day (TCID50), among the MITT subset of subjects with positive viral culture results at Baseline.

The independent variables (PK exposure parameters) will include serum VIS410 AUC and  $C_{\max}$ . Univariable analyses will be conducted to explore the relationship between independent variables and dependent, as summarized above. Various techniques will be used to explore exposure-response relationships. These techniques may include graphical and statistical methods, including the creation of boxplots, spaghetti plots, histograms, and a variety of linear, nonlinear, or logistic regression techniques and time-to-event methods, as appropriate. Decisions with

January 17, 2019

regards to methods used will be based on the nature of the data, and strengths of relationships identified via graphical evaluation. If appropriate, continuous independent variables will be evaluated as such, and also as categorical variables (grouping subjects into exposure categories). Categories based on subject groupings will include quartiles, but also the implementation of Classification and Regression Tree Analysis (CART) to identify significant target breakpoints. Results of the exploratory analyses may be reported in the clinical study report, or may be reported separately.

#### **11.4 Exploratory Analysis of PK and Virology in Tracheal Aspirates**

Exploratory analyses will be performed to evaluate the difference in VL (qRT-PCR and TCID50) between VIS410 + oseltamivir and oseltamivir alone treatment groups in tracheal aspirates. VL (qRT-PCR and TCID50) will be compared between nasopharyngeal samples and tracheal aspirates obtained from the same subjects. VIS410 concentrations (PK) will be compared in serum, nasopharyngeal, and tracheal aspirates obtained from the same subjects. Relationships between VIS410 and viral load in tracheal aspirates may also be assessed.

#### **11.5 Exploratory Analysis of PK and Anti-drug Antibodies (ADA)**

Exploratory analyses will be performed to evaluate the following serum and nasopharyngeal endpoints by ADA status:

- Cmax (ng/ml)
- Tmax (day)
- Tlast (day)
- AUC0-∞ (day\*ug/mL)
- AUC%extrap (%)
- AUC0-last (day\*ug/mL)
- t1/2 (day)
- CL (ml/day) (serum only)
- Vd (ml) (serum only)

#### **11.6 Anti-drug Antibodies**

Summaries of anti-VIS410 antibody titers will be presented by treatment group and time point using descriptive statistics. Anti-VIS410 antibody titer results will be summarized as negative/positive; the ADA positive category includes subjects with >4 fold change, the ADA negative category includes subjects with no more than a 4-fold change from baseline. Overall positivity will be based on the subject being ADA positive at any post-baseline timepoint; negativity will be based on the subject being ADA negative at all assessed post-baseline timepoints.

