1.3.1.2 Safety Results

In the Phase 1 study, VIS410 was administered IV over 2 hours. Overall, VIS410 was generally safe and well tolerated at all dose levels studied. TEAEs were reported for 20 of 30 subjects (66.7%) receiving VIS410 and 7 of 11 subjects (63.6%) receiving placebo. There were no drug-related SAEs, no drug-related discontinuations, and no infusion-related reactions, such as anaphylaxis or injection site reactions.

Notable AEs included one unrelated SAE of leukopenia and esophagitis secondary to primary herpes simplex virus-1 infection in 1 subject (VIS410, 30-mg/kg cohort). This SAE resolved, and the subject did well. Another unrelated SAE of acute appendicitis was also reported (placebo cohort).

The most common AEs observed were diarrhea (10 of 41 [24.4%]) and headache (8 of 41 [19.5%]; 5 subjects received VIS410). All diarrheal or loose stool AEs were observed in the VIS410-treated subjects and were usually mild to moderate, started ~2 to 4 hours after dosing, were transient, and resolved spontaneously within 24 hours after dosing with no associated dehydration. There were no associated elevations in alanine aminotransferase, aspartate aminotransferase, or bilirubin parameters.

Mean hematology, serum chemistry, and urinalysis results were within the normal limits, and the mean values and changes from baseline were similar across the treatment groups and placebo.

Overall, mean vital sign measurements observed after dosing were similar to those observed at baseline. Mean changes from baseline were also similar across VIS410 dose levels, and no apparent treatment- or dose-related trends were observed.

The antidrug antibody (ADA) data demonstrated a low level of positive ADA in 4 out of 30 subjects receiving VIS410 (Table 2). The subjects with positive ADA did not demonstrate any impact on their PK profile.

Table 2. Summary ADA Data – Phase 1 Study VIS-C001

Cohort Dose (mg/kg)	No. of Confirmed ADA Positive	Pre-infusion Titer	Confirmed Day	Positive Titer
2	0/6	None detected	NA	None detected
		None detected	120	Titer 10
5	3/6	None detected	14	Titer 10
		None detected	120	Titer 40
		None detected	120	Titer 40
15	1/6	None detected	120	Titer 40
30	0/6	None detected	NA	None detected
50	0/6	None detected	NA	None detected

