## 4.2 Missing Data Conventions

Partial and missing AE and concomitant medication dates will be imputed with maximum conservatism. If the onset date is missing or partial, the date will be compared as far as possible with the date of first dose of study medication. If no month is present and it is in the same year as the date of first treatment, or the year and month are the same as the first treatment date, the onset date will be imputed as the date of first treatment. Otherwise it will be imputed as 01 January in the available year, or the first day of the month and year available. End dates will be imputed as 31 December in the available year, or the last day of the available month and year collected. Partial dates will be presented in listings, along with classifications of TEAE for AEs or Prior/Concomitant/Both for medications.

Missing data will generally be left as missing, except for partial and missing AE and concomitant medication dates. Special cases, e.g. below the limit of quantification, will be described in the sections that describe the specific parameter's analysis.

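### The more-than-4-fold rule for ADA positivity gives no value for an undetected baseline and can class a new antibody response as negative

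*SAP*

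**What the plan says.** SAP 11.6 splits subjects by fold change alone: "the ADA positive category includes subjects with >4 fold change", and "the ADA negative category includes subjects with no more than a 4-fold change from baseline". A subject is positive overall if positive at any assessed time after baseline. The section has no category for a subject who goes from no detectable antibody to a detectable one, and no number for an undetected result.

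SAP 4.2 places that detail in the section for each parameter: "Special cases, e.g. below the limit of quantification, will be described in the sections that describe the specific parameter's analysis". SAP 11.1 supplies it for the anti-influenza HAI titers: "Values that are <10 (LLOQ) will be assessed as 5". SAP 11.6 has no counterpart for ADA.

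ADA status is then used in SAP 11.5: "Exploratory analyses will be performed to evaluate the following serum and nasopharyngeal endpoints by ADA status". It also defines Table 14.4.2.10.1 (positive versus negative) and Tables 14.4.1.3 and 14.4.1.6 (serum and nasopharyngeal PK parameters by ADA status).

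Protocol 1.3.1.2 reports a "low level of positive ADA in 4 out of 30 subjects receiving VIS410" in the Phase 1 study. In Table 2 the pre-infusion entry for each of these subjects is "None detected", and the later titers are 10 or 40.

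**The concern.** A fold change suits a subject who already has a measurable titer that rises. For a subject with nothing measurable at baseline, the ratio is either undefined or set by whatever number replaces the undetected result. That second kind of subject is the only kind of positive in the Phase 1 table, so it is the case the rule should be expected to meet. The protocol counts those subjects as positive; the SAP rule may not.

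Immunogenicity is a secondary objective (Protocol 2.2, SAP 2.4.2). A treatment-induced positive that fails the fold rule is missing from the ADA rate. It also enters the negative group of the PK comparison, where it would dilute any effect of ADA on exposure.

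**Working it through.** **Plan's own figure.** Table 2 by cohort: 0/6 + 3/6 + 1/6 + 0/6 + 0/6 = 4/30 = 13.3%. This agrees with the 4 of 30 in the protocol text.

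**Inputs.**
- Rule (SAP 11.6): positive if post-dose titer / baseline value > 4; negative if ≤ 4.
- Baseline of the Phase 1 positives: none detected. Let *b* be the number given to that result. The SAP states none for ADA, so *b* is an assumption, varied here from 1 to 10. The nearest analogue in the SAP is 5 (HAI, SAP 11.1), which is not written for ADA.
- Post-dose titers (Table 2): 10 or 40.
- Row layout: Table 2 appears to print four titer rows for the three positive subjects at 5 mg/kg (10 at Day 120, 10 at Day 14, 40 at Day 120, 40 at Day 120) and one row at 15 mg/kg (40 at Day 120). The layout may have been disturbed in the text copy. Reading A takes the three Day 120 rows as the three subjects, so the four titers are 10, 40, 40, 40. Reading B takes one titer-40 row as a duplicate, so they are 10, 10, 40, 40.

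**Where the classification changes.**
- Titer 10 is positive only if 10/*b* > 4, that is *b* < 10/4 = 2.5.
- Titer 40 is positive only if 40/*b* > 4, that is *b* < 40/4 = 10.

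**Results for the 4 Phase 1 positives.**
- *b* = 10: 10/10 = 1 and 40/10 = 4, and neither exceeds 4. Positive: 0 of 4, so the rate is 0/30 = 0%.
- *b* = 5: 10/5 = 2 (negative) and 40/5 = 8 (positive). Positive: 3 of 4 on reading A (3/30 = 10.0%), or 2 of 4 on reading B (2/30 = 6.7%).
- *b* = 1: ratios of 10 and 40. Positive: 4 of 4, or 13.3%.
- *b* = 0 or missing: the ratio is undefined and the subject cannot be classified.

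**Effect of the strict inequality.** With a cut-off of at least 4-fold, *b* = 10 gives 3 of 4 positive (2 of 4 on reading B) instead of 0. At *b* = 5 the two cut-offs give the same result.

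**Relevance to this trial's follow-up.** The study ends at Day 56 (Protocol 4.2), and no ADA sample is scheduled later. The only positive row in Table 2 dated within that period is the Day 14 row, titer 10. It is 2-fold at *b* = 5 and 1-fold at *b* = 10, so it is negative at both.

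**The case against.** Four objections have weight.

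First, a reader might infer that most or all Phase 1 type conversions would be lost and that 13.3% would fall to 0%. The documents do not support that. It requires an undetected baseline to be set to 10, and neither document gives that value. At 5, the SAP's own convention for another titer, only the titer-10 results are lost; at 1, none are.

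Second, the Phase 1 numbers transfer poorly. All but one of the positive rows are dated Day 120, beyond this trial's last visit, so most of those subjects might not have been detected here under any rule. Phase 1 sampling days are not given. This stands, and it limits the figures to an illustration.

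Third, a reader might infer that the rule conceals antibody responses altogether. It does not. SAP 11.6 also summarises titers by group and time, Table 14.4.2.10.3 gives titer categories, and Listing 16.2.10.1 gives individual ADA data. Table 14.4.2.10.2 gives fold increase, although it needs the same missing baseline value. These outputs let a reader see a conversion, but they do not correct the positive/negative rate or the PK split.

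Fourth, the PK comparison is exploratory, and the protocol reports no visible effect of ADA on PK in the Phase 1 positives. Nothing in the documents shows that a PK conclusion would change. Choosing more than 4-fold over at least 4-fold is also a legitimate preference, and SAP 11.6 states both sides of it consistently. The difficulty is the undetected baseline, not the strict inequality by itself.

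**Conclusion.** The point holds in a limited form. As written, SAP 11.6 cannot classify a subject with undetected ADA at baseline, and some ways of filling the gap would class a real undetected-to-detected conversion as negative. Applied to the 4 Phase 1 positives, between 0 and 4 would be classed negative, depending on a value the SAP does not state. With the SAP's HAI analogue of 5, the number is 1, or 2 on the other reading of Table 2.

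This is more than a missing detail. Under that natural choice, a subject the protocol would call positive joins the negative group. The consequence is confined to the ADA rate and the exploratory PK split by ADA status. The conclusion assumes that ADA responses in this trial resemble those in Phase 1 (none before dosing, low titers after); the size of any misclassification here cannot be predicted from the documents.

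**What to change.** In SAP 11.6, define ADA positive as either of two cases:
- **Treatment-induced:** no detectable ADA at baseline and a positive post-dose sample.
- **Treatment-boosted:** positive at baseline, with a rise that meets the stated fold threshold.

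Use this status in Tables 14.4.2.10.1, 14.4.1.3 and 14.4.1.6. State the value used for an undetected baseline in the fold-increase table (14.4.2.10.2). Because neither document sets out how a sample is called positive in this trial, add a reference to the laboratory's criterion.

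This rule classes all 4 Phase 1 cases as the protocol did, and the positive/negative split no longer depends on an assigned baseline number. The cost is SAP wording, with no new data collection. The small downside is that the reported ADA rate may be higher.
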